8.2.5 Prognostic factor analyses

Data of this trial will be included in the EORTC Brain Tumor data warehouse for further pooled data analyses of prognostic factors, prognostic models development and subgroup analyses.

8.2.6 Data re-coding and display

Frequency tables will be tabulated (by treatment group or otherwise) for all categorical variables by the levels of the variables as they appear on the CRF (with %). Categories with a text field specification will be tabulated as categories and then supplemented by a listing with the following information for the patients fulfilling the condition for the specification (patient id, institution, treatment group, value of the item and text field contents).

Dates relating to events prior to entry will be presented as the delay in days (or weeks, months, or years) between the past event and the date of entry (date of randomization – date of past event + 1) and presented using the median and range. For example, on the randomization checklist, the date of last administration of prior treatment (or the date of first diagnosis of the cancer) will be presented as the time elapsed (in days, weeks, months or years, as appropriate) since the day of the last administration and the date of entry on study (date of randomization – last administration/diagnosis +1).

Other delays (e.g. re-treatment delays) are presented as continuous variables using the median and range.

Continuous variables for which a coding system exists (such as for laboratory data) will be recoded into categories (for adverse events, the grading scale specified in the protocol will be used). Whenever no specific scale exists, lab data will be categorized based on the normal range: for example, below the lower normal limit (when appropriate), within the normal range, above the upper normal limit (ULN) and the degree to which it is above the ULN (for example > 2.5 x ULN, > 5 x ULN, > 10 x ULN). For laboratory data, the nadir is generally displayed. The nadir in a given cycle is the lowest laboratory value in that cycle; the overall nadir for a patient is the lowest laboratory value among all cycles.

Other continuous variables (for example age, dose ...) are presented using the median and range (minimum, maximum) and Mean (Standard Deviation).

If appropriate, continuous data may also be presented in categories (for example, age may also be grouped in decades).

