1.2 Trabectedin

The anticancer compound trabectedin (ET743, trade name: Yondelis) (Ref. 2) is a tetrahydroisoquinoline molecule originally isolated from the sea squirt *Ecteinascidia turbinata* (Ref. 3). The mode of action of trabectedin is not completely understood. However, it is known that the drug binds to the minor groove of the deoxyribonucleic acid (DNA) double helix forming trabectedin-DNA adducts that bend the DNA towards the major groove. Furthermore, trabectedin might affect diverse DNA binding proteins including several transcription factors and DNA repair mechanisms. The alterations induced by the drug activate the nucleotide excision repair (NER) pathway, which is required for maximum activity of trabectedin, while its activity is retained in mismatch repair-deficient cells. In vitro studies elucidated that trabectedin selectively inhibits the transcription of several genes, particularly those encoding the multidrug resistance protein 1, heat shock protein 70, and the cyclin-dependent kinase inhibitor p21WAF1/Cip1 contributing to the induction of programmed cell death. In addition, trabectedin has been shown to deplete tumor-associated macrophages and act as an anti-angiogenic agent (Ref. 3, Ref. 4, Ref. 5, Ref. 6).

Trabectedin has been shown to be active against a wide variety of cell lines and xenografts derived from several solid tumor types. In early clinical trials, trabectedin was active against several solid tumors including breast cancer, prostate cancer, renal cancer, melanoma, and non-small cell lung cancer.

As of 1 July 2013, approximately 9,015 subjects with advanced malignancies have been treated with trabectedin, administered either as a single agent or in combination with other chemotherapeutic agents (Ref. 2). Trabectedin is generally well tolerated with manageable and mostly reversible adverse effects like transaminase elevations, myelosuppression, nausea, emesis, and fatigue. Creatine phosphokinase/kinase elevations (based on laboratory values) and rhabdomyolysis are also observed.

Trabectedin is an emetogenic drug and prophylactic anti-emetic treatment is recommended.

Trabectedin has been approved and is routinely used in patients with advanced soft-tissue sarcoma (STS) who have failed or are not eligible for first line therapy with anthracyclines and ifosfamide and in patients with platinum-sensitive recurrent ovarian cancer in combination with pegylated liposomal doxorubicin.

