5.6.1.2 Re-treatment criteria

- ◆ A maximum delay of 3 weeks from the due date for next infusion is allowed for recovery from toxicity in the preceding cycle of treatment.
- ◆ The following criteria should be met before the next infusion:

Hematological parameters	Value at day 1 of new treatment cycle
Hemoglobin	≥ 9 g/dL or ≥ 5.6 mmol/L
Platelet count	$\geq 100 \times 10^9$ /L
Neutrophil count	$\geq 1.5 \times 10^9$ /L
Serum chemistry parameters	Value at day 1 of new treatment cycle
Creatinine clearance	≥ 30 mL/min
Creatine phosphokinase	$\leq 2.5 \times$ ULN
Total bilirubin	\leq ULN
ALT or AST	$\leq 2.5 \times$ ULN
Alkaline phosphatase	$\leq 2.5 \times$ ULN
Albumin	≥ 25 g/L
Non hematological – non serum chemistry parameters	Status at day 1 of new treatment cycle
Severity of other adverse event has to recover to \leq Grade 1	

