8.2.3.4.2 Biochemical parameters

The worst value of each biochemical category will be identified and graded for each patient. Frequencies and percentages of each category will be tabulated. A table with grade 3/4 frequencies and percentages will be provided.

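### Section 8.2.6 displays the lowest laboratory value, which is the least toxic one for ALT, AST, bilirubin, ALP, CPK and creatinine and conflicts with the worst-value tables; a minor wording error

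*Combined protocol and SAP*

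**What the plan says.** Section 8.2.6 (Data re-coding and display) gives the general rule: "For laboratory data, the nadir is generally displayed. The nadir in a given cycle is the lowest laboratory value in that cycle". It continues at patient level: "the overall nadir for a patient is the lowest laboratory value among all cycles". It names no parameters and makes no exception for those where a high value is the harmful one. The sentence just before it sorts laboratory values that lack a specific scale by their distance above the normal limit, with 2.5, 5 and 10 times the ULN as example cut-offs. The paragraph therefore covers chemistry as well as blood counts.

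The safety sections set a different rule. For chemistry, section 8.2.3.4.2 says: "The worst value of each biochemical category will be identified and graded for each patient". It adds: "A table with grade 3/4 frequencies and percentages will be provided". Section 8.2.3.4.1 does the same for hematology. Section 7.2.2 has the sponsor compute each patient's maximum CTCAE grade in each cycle. Sections 8.2.3.4.3 to 8.2.3.4.5 tabulate worst grades of adverse events, serious adverse events and related adverse events.

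**The concern.** A nadir is the natural summary for neutrophils, platelets or hemoglobin, where low is harmful. For liver enzymes, bilirubin, CPK and serum creatinine, harm is a rise, so the lowest value is the patient's best. Section 1.2 describes trabectedin as having "manageable and mostly reversible adverse effects like transaminase elevations, myelosuppression, nausea, emesis, and fatigue", and section 5.6.1.6 deals with severe CPK elevation. These are the parameters for which the rule points the wrong way.

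What is at stake is the consistency of the safety report. A programmer who follows 8.2.6 would produce chemistry displays with little or no elevation, next to graded tables from the same data that show the peaks. Section 8.2.3.4 plans no tests or confidence intervals for safety, so readers depend on the descriptive displays agreeing with each other.

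**Working it through.** The plan gives no figure to reproduce. The check is to compare the rules and then derive one bound.

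**1. Direction of harm, from the protocol's own limits**

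| Parameter | Harmful direction (source) | Lowest value is | 8.2.6 agrees with the worst-value rule? |
|---|---|---|---|
| Neutrophils, platelets | low (5.6.1.1) | worst | yes |
| Hemoglobin, albumin, creatinine clearance | low (lower limits in 5.6.1.2) | worst | yes |
| ALT, AST, bilirubin, ALP | high (5.6.1.1) | best | no |
| CPK | high (5.6.1.6) | best | no |
| Serum creatinine | high (upper limit in section 3) | best | no |

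The two rules agree where low is worse and name opposite extremes where high is worse.

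**2. Bound for re-treated trabectedin patients**

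Inputs:
- Section 5.6.1.2 states: "The following criteria should be met before the next infusion". Its table requires ALT/AST and CPK at or below 2.5 x ULN, and bilirubin at or below ULN, on day 1 of the new cycle.
- Section 6.3 requires chemistry on day 1 of each cycle or within 72 hours before.

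Let x₁, …, xₙ be a patient's on-study values of one parameter, in multiples of ULN, and let x_g be the value that cleared the patient for a second or later infusion. Then

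min(x₁, …, xₙ) ≤ x_g ≤ 2.5 for ALT, AST and CPK, and ≤ 1 for bilirubin.

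The peak does not enter this inequality.

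**3. Illustration (assumed values)**

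Take ALT of 1, 12, 4 and 2 x ULN on days 1, 8, 15 and 22.
- Display under 8.2.6: min(1, 12, 4, 2) = 1 x ULN.
- If day 1 is treated as baseline and left out: min(12, 4, 2) = 2 x ULN, still within 2.5.
- Value graded under 8.2.3.4.2: max(1, 12, 4, 2) = 12 x ULN.

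**4. Limits of the bound**

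- It covers only trabectedin patients with at least two infusions. Section 5.6.1.2 sits under 5.6.1 (Trabectedin), and no equivalent gate is stated for the control arm.
- It is not strict for ALP. Section 5.6.1.2 sets 2.5 x ULN, but section 6.3 foresees day-1 ALP above that level with follow-up tests in the normal range.
- It does not cover serum creatinine, which has no re-treatment limit of its own; only clearance does.

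Outside the bound, the lowest value is still the wrong extreme for every parameter in the last three rows of the table.

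**5. Sampling by arm**

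Section 6.3 adds weekly chemistry in the first two cycles for the experimental arm only. Extra samples can only lower a minimum or leave it unchanged, so a lowest-value display tends to flatter trabectedin. The reverse holds for a maximum, so this asymmetry is a caveat on any display of extremes and is not removed by the fix.

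**The case against.** The strongest reply is that nothing is lost. The safety sections govern the safety analysis. They grade the worst chemistry value per patient, provide a grade 3/4 table, take the highest grade per cycle and tabulate worst adverse event grades. Sections 6.1, 6.3 and 6.4.1 also have abnormal values of chemistry parameters not on the form recorded as adverse events. Section 8.2.6 is a generic convention softened to a default: "For laboratory data, the nadir is generally displayed". Dose decisions rest on observed values, not on these displays.

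Most of this stands. A reader might infer that the rule would hide liver and muscle toxicity. The documents do not support that, because the peaks remain in the graded and adverse event tables.

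A reader might also infer that the categories above 2.5, 5 and 10 x ULN would be empty for re-treated patients. That does not follow either. Those categories apply only to parameters without a specific scale, while 8.2.3.4.2 says biochemistry is graded. Nor does 8.2.6 say that the nadir feeds them.

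The reply does not remove the inconsistency itself. The softening word permits exceptions without saying when or for which parameters. Section 8.2.6 is also the only place that says which per-cycle and overall laboratory value to display, and for these parameters it names the wrong one.

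**Conclusion.** Wrong as written, minor. For ALT, AST, bilirubin, ALP, CPK and serum creatinine, a display built on 8.2.6 shows the least toxic value and contradicts 8.2.3.4.2 and 7.2.2. For re-treated trabectedin patients the displayed overall ALT, AST and CPK cannot exceed 2.5 x ULN, whatever the peak.

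The bound assumes that the re-treatment rule was followed, that the ALT/AST row applies to both enzymes, and that the clearing sample is recorded and counted in some cycle. The wider finding, that the lowest value is the wrong extreme, needs none of these assumptions.

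The effect stops at the supplementary laboratory display. No efficacy endpoint, analysis population, sample size or error rate changes.

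**What to change.** Replace the two nadir sentences in 8.2.6 with:

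> *For laboratory data, the worst value in the direction of toxicity is displayed per cycle and overall (lowest where low is worse, highest where high is worse, both where CTCAE grades both directions), for the parameters collected on the CRF, consistent with 7.2.2, 8.2.3.4.1 and 8.2.3.4.2.*

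The restriction to CRF parameters is needed. Section 6.4.1 lists only some chemistry tests as collected on the form at that visit, and sections 6.1 and 6.3 also refer to parameters that are not. Albumin, electrolyte and glucose values may therefore not be in the database.

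The cost is two sentences, made before the tables are programmed. No new data are needed, no clinical rule changes, and blood-count displays stay as they are. Separately, the ALP wording in sections 5.6.1.2 and 6.3 should be reconciled; this point takes no view on which is right.

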8.3 Interim analyses

A futility interim analysis based on boundaries from Rho family ($\rho=1.625$) is planned when half of events (36) are observed. This should occur about 14.5 months after start of accrual when 61 patients are recruited. In absence of effect i.e. an observed PFS HR ≥ 1 , trial would be stopped for futility. With this boundary, there is 50% chance to stop the trial for lack of effect if the null hypothesis is true (H0). Safety will be reviewed by the EORTC DSMB every 6 months and by the EORTC IDMC at the time of futility analysis together with efficacy data.

8.4 End of study

End of study occurs when all of the following criteria have been satisfied:

1. Thirty days after last treatment administration to the last patient on protocol
2. The trial is mature for the analysis of the primary endpoint as defined in the protocol
3. The database has been fully cleaned and frozen for this analysis

Follow up data might be captured for all patients after the end of study declaration in order to document secondary endpoints with more precision i.e. overall survival, outcome of patients according to molecular and pathological subgroups (see chapter 8 and 11).

9 Data Monitoring

Safety data are reviewed within the EORTC Headquarters on a regular basis as part of the Medical Review process. Problems which are identified will be discussed with the Study Coordinators who will take appropriate measures. Safety information will also be included in trial status reports which serve as a basis of discussion during EORTC Group meetings. These reports will be made available to investigators participating in the study.

The EORTC Independent Data Monitoring Committee (IDMC) will review all safety problems identified by the EORTC Headquarters for which an advice is sought. Experts on the IDMC performing this review will be selected to have the relevant early trials/drug development expertise and will provide a review process independent of that of the Medical Review. In principle, no access to outcome data is necessary for safety reviews. However, the IDMC will also provide recommendations as an initial step in phase III trials to advise if a full review of all study data and endpoints is needed.

The EORTC IDMC is charged with the interim review (planned in the protocol or ad hoc) of randomized phase II and phase III studies. When interim analyses are carried out, the interim monitoring of efficacy and safety data is performed according to the Statistical Considerations chapter in this protocol and EORTC Policy 004 on “Independent Data Monitoring Committees and Interim Analyses”.

The results of the interim analyses are confidential and are discussed by the EORTC IDMC. The IDMC will subsequently recommend to the EORTC Group whether any changes should be made to the study.

No efficacy results will be presented at EORTC Group meetings or elsewhere before the trial is closed to recruitment and the data are mature for the analysis of the primary endpoint, unless recommended otherwise by the EORTC IDMC.

10 Quality of life assessment

Relatively little is known about the health-related quality of life (HRQoL) of meningioma patients. This is remarkable considering the growing interest in incorporating HRQoL as secondary outcome measure in primary brain tumor clinical trials (Ref. 14). Data that do exist mainly concern WHO grade I meningioma patients. Patients with suspected WHO grade I meningioma already have limitations in cognitive functioning and HRQoL (Ref. 15), while HRQoL slightly improved after surgery in a mixed group of WHO I-III patients (Ref. 16). Van Nieuwenhuizen et al did not demonstrate any differences in HRQoL between WHO I meningioma patients who had undergone surgery with or without postoperative irradiation on the one hand, and age-, gender-, and education-matched healthy controls on the other hand (Ref. 17). Another study confirmed that HRQoL long-term outcome of the majority of WHO grade I meningioma patients is comparable to that of the general population, except for role limitation caused by physical functioning. However, patients with cognitive deficits and those using anti-epileptic drugs (AEDs) had a compromised HRQoL (Ref. 18). Altogether, currently the scarce available data suggest that HRQoL might initially be compromised in meningioma patients, but is comparable to healthy controls when adequate treatment has been installed, apart from a subgroup of patients with severe cognitive deficits or on AED. Unfortunately, no specific data on HRQoL of WHO grade II and III patients are available.

Evaluation of HRQoL is important to get a better understanding of the balance between the effects of treatment response and treatment-related side-effects from the perspective of the patients. The role of chemotherapy in WHO II and III meningioma is far from being established. The major endpoint in the current randomized phase II trial is to compare PFS between the experimental (trabectedin) and the control arm (local standard of care) for patients with a poor prognosis. Trabectedin has been shown to be well tolerated with manageable and mostly reversible adverse effects such as transaminase elevations, myelosuppression, nausea, vomiting and fatigue. Only few patients experience severe toxicities like skin and soft tissue necrosis due to extravasation or rhabdomyolysis. If treatment-related side effects influence the HRQoL of the patients in a negative way, however, possible advantages in terms of PFS will have to be balanced against the burden of treatment. It is for this reason that HRQoL is included as a secondary endpoint in this study.

10.1 Objective

The study hypothesis is that trabectedin chemotherapy will result in a PFS-6 of 35% compared to 15% in the control arm. In the present study, HRQoL is an important secondary endpoint. The main objective of HRQoL assessment within this trial is to determine the impact of trabectedin on **seven chosen domains being primarily global QoL, with role functioning, physical functioning, cognitive functioning, fatigue, diarrhea, and nausea and vomiting as secondary key issues**. It is expected that these were likely to be most affected in patients undergoing trabectedin chemotherapy. The Ho hypothesis will be tested to show that there is no difference between patients in both arms during and after treatment for the selected scales. A secondary objective is to evaluate the effect of the treatment on the remaining symptoms and functioning scales as treatment-related side effects may have a (temporary) negative influence on the health related domains of HRQoL of these patients.

10.2 HRQoL instrument

Quality of life will be assessed with the EORTC Quality of Life Questionnaire (QLQ-C30) version 3. This instrument is composed of multi-item and single-item scales. These include five functional scales (physical, role, emotional, social, and cognitive), three symptom scales (fatigue, nausea and vomiting and pain), a global health status/QoL scale, and six single items (dyspnea, insomnia, appetite loss, constipation, diarrhea and financial difficulties). All scales and single items meet the standards for reliability. The reliability and validity of the questionnaire is highly consistent across different language-cultural groups. (Ref. 19, Ref. 20, Ref. 21) The average time to complete the questionnaire is approximately 10 minutes. The EORTC QLQ-C30 version 3 has been translated in over 50 languages according to a standardized translation procedure.

The domains of interest as specified in the previous paragraph are covered by the Global QoL/health, role functioning, physical functioning, cognitive functioning, fatigue, diarrhea, and nausea and vomiting scales.

In order to address particularities and special dimensions that pertain to the HRQoL issues in brain tumors, the QLQ Brain Cancer module (QLQ-BN20) will be added to the HRQoL evaluations in this trial. This module has been developed specifically for use in brain tumor patient populations. The QLQ-BN20 has shown its validity and utility. (Ref. 20, Ref. 21) The module consists of 20 items, grouped into 4 domains (future uncertainty, visual disorder, motor dysfunction and communication deficit) and 7 single items (headaches, seizures, drowsiness, hair loss, itchy skin, weakness of legs and bladder control).

10.3 Study design

Patients are eligible for the quality of life assessment in this study if they fulfill the eligibility criteria (Chapter 3) and, complete the baseline HRQoL questionnaire before randomization. Patients will be informed in the written patient informed consent form that they will have to undergo repeated quality of life assessments while involved in this trial. HRQoL will be a secondary endpoint and evaluated in a longitudinal design in all patients entered in this study. HRQoL is a mandatory requirement.

10.3.1 HRQoL schedule - timing and location

HRQoL questionnaires must be filled out at the hospital when patients come for a scheduled visit according to the EORTC “Guidelines for administration of questionnaires” (see Appendix G). The pre-treatment questionnaires must be filled within 4 weeks prior to randomization. Subsequent questionnaires are filled in as described in the time schedule in this paragraph.

Electronic copies of the HRQoL questionnaires will be sent to the institutions to be printed. Additional translations can be provided to any institution upon request via the EORTC contact person. The case report forms will include a question whether the HRQoL forms have been filled in, and if not, the reason why. The questionnaire will be handed out to the patients by the investigator or a study nurse prior to seeing the doctor for clinical evaluations. The patient should complete the questionnaires by her/himself in her/his own language **prior** to seeing the treating physician at the outpatient clinic as completely and accurately as possible. It is recommended that a key person (e.g. research nurse) at each center should be responsible for questionnaire data collection in order to optimize the compliance of the patient and to ensure the completeness of the data.

During the study, compliance with completing questionnaires will be investigated at each time point. The compliance of the HRQoL assessments will also be reviewed twice a year and will be part of the descriptive report.

The time windows for eligible HRQoL assessments will be as follows:

Assessment	Time window
Baseline	Can be completed before or on the day of start of protocol treatment but no earlier than 28 days before.
Week 3 (End of cycle 1)	To be completed during the third week after treatment start while on protocol treatment. If 3 weekly chemotherapy regimen: can be completed during the third week of the first cycle of chemotherapy (D15-D21 of cycle 1).
Week 6 (End of cycle 2)	To be completed during the sixth week after treatment start while on protocol treatment. If 3 weekly chemotherapy regimen: can be completed during the third week of the second cycle of chemotherapy (D15-D21 of cycle 2).
Week 12 (End of cycle 4)	To be completed during the twelfth week after treatment start while on protocol treatment. If 3 weekly chemotherapy regimen: can be completed during the third week of the fourth cycle of chemotherapy (D15-D21 of cycle 4).
At 6 months	Can be completed at any time during the fifth and sixth month after date of randomization regardless of treatment or progression status.

